**The legend and footnotes for Table 1 through Table 5 are listed below.**

ACQ-7=Asthma Control Questionnaire; Ad=admission; ADA=anti-drug antibody; AE=adverse event;  $\beta$ -HCG=beta human chorionic gonadotrophin; BMI=body mass index; CGI-C=Clinician Global Impression of Change; COVID-19=Coronavirus disease 2019; D=day; Di=discharge; ECG=electrocardiogram; FeNO=fractional exhaled nitric oxide; FSH=follicle stimulating hormone; IFN  $\lambda$ =interferon gamma; IgE=immunoglobulin E; IL=interleukin; IP-10= interferon gamma-induced protein 10; NAbs=neutralizing antibodies; PK=pharmacokinetic; SOP=Standard Operating Procedures; TARC=thymus and activation-regulated chemokine; TB=tuberculosis; TSLP=thymic stromal lymphopoietin [REDACTED]=every [REDACTED] weeks; [REDACTED]=every [REDACTED] weeks; [REDACTED]=every [REDACTED] weeks; W=week.

a In women of childbearing potential at Visit 2 and at the Final Visit a serum  $\beta$ -HCG pregnancy test will be performed. At other visits a urinary pregnancy test will be performed. Follicle stimulating hormone will be assayed in women who on Visit 1 fit the post-menopausal criterion included in Section 4.8.4.

b A symptom-driven physical examination will be performed as needed based on reported signs and symptoms.

c Vital signs will be body temperature, pulse, respiratory rate, and blood pressure. See Table 9 for timing of assessments on dosing days.

d ECG assessments will be performed prior to any blood draws, FeNO measurements, and/or study drug administration. See Table 9 for timing of assessments on dosing days. All ECGs are performed in triplicate.

e Spirometry on Screening Visits 1 and 2 will be conducted at 60 minutes and 30 minutes prior to bronchodilator administration and at 30 minutes post-bronchodilator. At Visit 4 (Day 1) and at subsequent dosing visits, spirometry will be conducted approximately 60 minutes and 30 minutes prior to dosing (See Table 8). At non-dosing visits where spirometry is conducted, 2 assessments will be conducted 30 minutes apart; assessments should be conducted at approximately the same time as on dosing days. No post-bronchodilator spirometry will be performed.

f Blood samples will be collected for assessment of haematology including eosinophils. On dosing days, samples will be collected pre-dose. Coagulation studies will be performed only at Visit 1 and the Final Visit.

g On dosing visits, chemistry and urinalysis laboratory tests will be collected pre-dose.

h On days where Spirometry is not performed, ACQ-7 question 7 will be answered based on the FEV1 value from the first measurement on the following morning

i Blood sampling for PK on dosing days will be collected pre-dose.

j Plasma levels of IL-5, IL-13, IFN  $\lambda$ , IL-17A, eotaxin-3, IP-10, and TSLP will be measured. Tryptase, carboxypeptidase, and TARC will also be measured.

k Subjects will be contacted by site personnel the day before each visit that includes a spirometric assessment to remind subjects of their visit and study rules. Subjects will also be contacted the day before their admission to the site.

l Flow cytometry samples will be collected and either analyzed or frozen. The decision to assay the frozen samples will be based on previous results.

m At Visit 5 (D2), Visit 6 (D4), Visit 16 (D86), Visit 17 (D88), Visit 18 (D92) and Visit 19 (D99) blood samples for haematology including eosinophils will only be collected for participants enrolled in Cohort 4.

n At Visit 5 (D2), Visit 6 (D4), Visit 16 (D86), Visit 17 (D88), Visit 18 (D92) and Visit 19 (D99) FeNO will be performed only for participants enrolled in Cohort 4.

#### **6.4. Interim Analysis / Data Monitoring**

An administrative interim analysis is planned for this study prior to the Primary Analysis. The results of the administrative interim analysis will have no impact on the trial design or analysis. A separate team will produce the results for this analysis and will have no further involvement in the study until after the study has been unblinded, see [Section 10.1.3](#).

A Safety Review Committee will take place before the first subject in each of Cohorts 1 and 2 receive their third dose. All safety data available at that point will be reviewed by the SRC. The outputs that will be produced for the SRC and the remit of the SRC will be defined outside of the SAP as part of the SRC charter.

## 7. STUDY ENDPOINTS

### 7.1. Primary Endpoint

The primary endpoints are AEs, SAEs, physical examinations, clinical laboratory assessments, vital signs, and electrocardiograms (ECGs). Subject withdrawals, early terminations, and dosing compliance are also assessed. These endpoints are evaluated in the Safety Population.

### 7.2. Secondary Endpoints

The secondary endpoints include UPB-101 anti-drug antibodies (ADAs) and serum UPB-101 concentrations and analyses including  $C_{max}$ ,  $t_{max}$ ,  $AUC_{tau}$ . If appropriate,  $AUC_{inf}$ ,  $t_{1/2}$ , apparent total body clearance after dosing (CL/F), and apparent volume of distribution during the terminal elimination phase after dosing (Vz/F), all after the first dose, will be analyzed as well. These endpoints are assessed from baseline through Week 24 in the PK Population.

### 7.3. Exploratory Endpoints

The exploratory endpoints include:

AEs, SAEs, pregnancy tests, and changes from baseline in physical examinations, clinical laboratory assessments, vital signs, and ECGs. Subject withdrawals, early termination, and dosing compliance are also assessed. Data collected from Baseline through Week 32 are included (data up to Week 24 are examined as part of the primary endpoints analysis). These endpoints are evaluated in the Safety Population.

UPB-101 ADAs, presence of neutralizing antibodies (Nabs) and serum UPB-101 concentrations and analyses including  $C_{max}$ ,  $t_{max}$ ,  $AUC_{tau}$ . Data collected from Baseline through Week 32 in the PK Population are included (data up to Week 24 are examined as part of the secondary endpoints analysis).

FeNO and blood eosinophil numbers from Baseline through Weeks 24 and 32. Total IgE; IL-5, IL-13, IL-17A, interferon gamma (IFN  $\lambda$ ), IFN  $\lambda$ -induced protein 10 (IP-10), TSLP, eotaxin-3, tryptase, carboxypeptidase, thymus activation regulated chemokine (TARC), C-reactive protein (CRP) concentrations; and flow cytometric assessments of phosphorylated signal transducer and activator of transcription (pSTAT) and receptor occupancy will be evaluated from Baseline through Weeks 24 and 32. These PD markers are evaluated in the PD Population.

Clinician Global Impression of Change (CGI-C) and Subject Asthma Control Questionnaire (ACQ-7) from Baseline through Weeks 24 and 32. These PD markers are evaluated in the PD Population.

Forced expiratory volume in 1 second (FEV1) from Baseline through Weeks 24 and 32. These PD markers are evaluated in the PD Population.

## 8. SAMPLE SIZE

The primary objective of the study is to assess the safety and tolerability of UPB-101 when administered as multiple ascending doses. A sample size of 40 subjects with 8 subjects per cohort (6 on active drug + 2 on placebo) is considered sufficient to meet this goal. The sample size is not based on formal statistical hypothesis testing.

## 9. STUDY ANALYSIS SETS

The populations defined below will be reviewed against the study database at a BDRM at the time of the Final Analysis. The database at this time will be nearly final (i.e., the meeting may result in further data queries/changes post meeting), so inclusion/exclusion of subjects from study populations defined at this meeting will be further checked (post meeting) against a final locked database and will then be finalised prior to unblinding.

The following populations are defined:

Population	Description
Safety Population	Subjects who receive at least 1 injection of study drug
Pharmacokinetic (PK) Population	Subjects in the safety population who have a baseline result and at least one post-baseline PK result and for whom at least 1 PK parameter can be estimated.
Pharmacodynamic (PD) Population	Subjects in the safety population who have a baseline result and at least one post-baseline biomarker result.

The primary endpoint analysis will be based on the safety population as it will consist of safety and tolerability endpoints. The PK and PD populations will be used to analyse the PK, and PD endpoints, respectively.

In each population, subjects will be analyzed in the treatment group corresponding to the treatment (i.e., dose of active UPB-101 or placebo) they actually received.

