9.4 Statistical Analyses

9.4.1 General Considerations

All safety, immunogenicity, PK, and PD data will be listed by subject. Unless otherwise specified, baseline is defined as the last observed measurement, whether scheduled or unscheduled, prior to the first dose of study drug.

UPB-101 treatment groups will be defined based on the cohort and dose assignment (e.g., [REDACTED]). The placebo treatment group will include all subjects assigned to placebo and will be pooled according to dosing regimen (e.g., Placebo [REDACTED], Placebo [REDACTED]) or, where appropriate, across all study parts.

No analysis windows will be defined. Data for repeatedly measured endpoints will be analysed according to the nominal visit. Summaries will be grouped by study part to maintain visit alignment across treatment groups.

Continuous variables will be summarized by UPB-101 dose group and pooled placebo, and by dosing frequency with descriptive statistics (e.g., number of observations, mean, standard deviation, median, interquartile range, maximum, and minimum). Categorical variables will be tabulated by frequency and percent of subjects per UPB-101 dose group and pooled

placebo, and by dosing frequency. Demographic data will be summarized by treatment, dose, and dose regimen. Analyses will be based on observed data only; no data will be imputed.

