- Clarification to management of Emergency Unblinding of Treatment Assignment. The Investigator is encouraged to discuss options with the blinded Medical Monitor and to notify the blinded Medical Monitor as soon as possible.
- Clarification for process of delivery of liver safety monitoring alerts from central laboratory and assessment of the parameters by the Investigator (Appendix 1).
- Correction of all references to Plasma UPB-101 concentrations to Serum UPB-101 concentrations.
- Correction to remove “serum” in all instances of total IgE measurements.

Version 6.0 was another non-substantial amendment which updated the following:

- Adjustment to the acceptable upper age limit from 55 to 60 years.
- Modification to the eosinophils requirement during the Screening Period, allowing for participants with eosinophil count  $\geq 150$  and  $< 200$  cells/ $\mu$ L to be considered in instances where their fractional exhaled nitric oxide (FeNO) is greater than 25 parts per billion (ppb) at either Visit 1 or Visit 2.
- Removal of the requirement for participants to be fully vaccinated against SARSCoV-2 (Coronavirus disease 2019 [COVID19]).
- Expansion of the window for later visits from  $+- 3$  to  $+- 5$  day.
- Replacement of the blinded medical monitor’s contact telephone number with a 24/7 telephone call cascade number.

Version 7.0 was a substantial protocol amendment and updated:

- Removal of language specifying cohort enrolment as parallel-sequential in nature. This change enables enrolment into Cohort 3 following partial enrolment into Cohort 2 due to the temporary halt to dosing.
- Updates to language related to Safety Review Committee which according to the original protocol would have been convened only between the second and third doses of Cohorts 1 and 2.

Version 8.0 was a non-substantial amendment and updated:

- Addition of timepoints for evaluation of the pharmacodynamic (PD) effect of UPB-101 biomarkers, specifically, the fractional exhaled nitric oxide (FeNO) and blood eosinophil numbers to participants enrolled in Cohort 4.
- Specification of the dose level and regimen to be administered to participants enrolled in Cohort 4.

- Extension of the estimated study end date to October 2023.

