#### 10.1.3. Data Presentation

The full list of TFLs to be produced for the final study analysis are shown in [Section 13](#), and the specific format and content of each data Table/Listing presentation is shown in [Section 14](#).

Summary Tables and Figures will be presented by treatment group (and also for an Overall column including all subjects, for selected data presentations). Within all Tables and Figures values for the treatment groups will be labelled as follows:

- [REDACTED] mg [REDACTED]
- [REDACTED] mg [REDACTED]

- [REDACTED] mg [REDACTED]
- [REDACTED] mg [REDACTED]
- Placebo and/or
- Screen Failures

An Overall column may be included in the disposition, and selected safety outputs which will include all treatment groups (Active and Placebo). Generally, the placebo groups will be pooled across all cohorts however, for some summaries placebo may be summarized according to dosing regimen (e.g. Placebo [REDACTED], Placebo [REDACTED] ) or treatment group (e.g. Placebo [REDACTED]).

For screen failures, data is only expected in a selection of datasets. The data collected within these datasets will be included in the relevant listings only. Additional data that may have been collected for screen failures, in error, will not be displayed in the participants listings. They will not be included in any summary tables.

For selected outputs the dosing regimen may be used in the summaries where cohorts of the same dosing regimen (i.e. [REDACTED], [REDACTED] ) will be grouped together, similarly cohorts may be grouped together by treatment group if there are multiple cohorts with the treatment group (e.g. [REDACTED] [REDACTED]), or summaries may be produced combining all of the active groups together. The ordering of treatment groups shown here represents the order in which they will appear in outputs.

The scheduled protocol visits will be labelled in (applicable) report presentations as follows:

- Screening: Visit 1
- Screening: Visit 2
- Screening: Visit 3
- Day 1
- Day X (where X is the protocol specified Day, to be included within summary Table)
- Week X (where X is the protocol specified study Week, to be included within summary Table)

Generally, the summaries will be produced by Day, although in some cases it may be preferable to summarize by Week. This will be specified within each of the shells, as appropriate.

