#### ***10.1.7. Examination of Subgroups***

No subgroup analyses will be undertaken.

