## **10.2. Participant Disposition**

The number of subjects randomized, treated, received all doses as planned, received all doses expected, completed the Week 24 visit, and completed the study will be tabulated by treatment group, as well as the number who withdrew from the study and/or discontinue treatment early. The data on subject disposition and informed consent will be listed.

Note it was possible for participants to be rescreened. In order to maintain the link between screen failures and their subsequent rescreen records these will be displayed as XXXX/YYYY in all relevant listings (where screen failure data are displayed), where XXXX is the final screening number given to the subject and YYYY is the screening number under which the data being displayed was collected.

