## **10.8. Investigational Product Exposure**

For each cohort the number and percentage of participants receiving each possible number of doses and injections will be tabulated. The details of each injection, including location and the reasons for incomplete and interrupted injections will be listed.

Planned Compliance will be calculated as: (the actual number of injections received / the number of injections planned given the assigned dosing regimen) \* 100.

Expected Compliance will be calculated as: (the actual number of injections received / the expected number of injections given the assigned dosing regimen and the conduct of the trial) \* 100.

The expected compliance accounts for the hold on dosing that occurred during the running of the trial during which subjects were not expected to have received any doses of study treatment, both will be listed.

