### **10.11.1. Biomarkers**

The biomarkers collected in the study include cytokines (IL-5, IFN λ, IP-10, TSLP, eotaxin-3, TARC and lab parameters (Eosinophils, Total IgE and C-reactive protein). Receptor occupancy evaluated by flow cytometry, considered as a biomarker for target engagement, is also included.

All biomarkers, with the exception of the flow cytometry biomarker, will be summarized by visit as absolute values, change from baseline and percentage change from baseline, by treatment group. Any scheduled pre-baseline data will also be summarized by visit and treatment group.

Flow cytometry based evaluation of receptor occupancy (free receptors) will be calculated as the difference between the signal intensity (measured as % of TSLPR+ CD14+ cells) of the test sample and an aliquot of the same sample incubated ex vivo with saturating levels of UPB-101 prior to adding the detection antibody. The receptor occupancy will then be summarized at each visit, along with the percentage of free receptors, where;

% free receptors at any timepoint (t) = (difference between signal intensity at timepoint (t) / difference between signal intensity at baseline )\* 100.

For negative % Free Receptors, set the value to 0. For % Free Receptors greater than 100%, set the value to 100%.

For all biomarkers the baseline will be the last non-missing result prior to first dose.

Any data that is below the limit of quantification will be replaced with zero before summarising but will be listed as '<BLQ'.

A mean plot of the biomarker results over time will be displayed, where the plots will display the mean at each visit +/- the standard error, with a line per treatment group.

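### The SAP lists no as-dosed display for subjects who lost doses in the hold, and its spirometry rule raises change from baseline at non-dosing visits

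*SAP*

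**What the plan says.** **The hold.** SAP Section 4 explains that protocol Version 7.0 let Cohort 3 open after "partial enrolment into Cohort 2 due to the temporary halt to dosing". SAP 10.8 defines compliance twice, against planned and against expected injections; the second figure "accounts for the hold on dosing that occurred during the running of the trial during which subjects were not expected to have received any doses". SAP 10.2 likewise counts separately those who "received all doses as planned, received all doses expected".

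**Grouping.** SAP Section 9 says "subjects will be analyzed in the treatment group corresponding to the treatment (i.e., dose of active UPB-101 or placebo) they actually received". SAP 10.1.3 adds "Summary Tables and Figures will be presented by treatment group" and lists four active labels (redacted), placebo and screen failures. Biomarkers, FeNO and spirometry, CGI-C and ACQ-7 (SAP 10.11.1 to 10.11.4) are all summarised by visit and treatment group, and the biomarker plots show "the mean at each visit +/- the standard error, with a line per treatment group". These endpoints run to Week 32 (SAP 7.3), on observed data (SAP 10.1.5). Protocol 9.4.1 states "No analysis windows will be defined. Data for repeatedly measured endpoints will be analysed according to the nominal visit", and SAP 10.1.7 states "No subgroup analyses will be undertaken".

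**Spirometry.** Under SAP 10.11.2, baseline is the 60-minute pre-dose reading at Visit 4. Later dosing days also use the 60-minute reading, and non-dosing days use the larger of the two readings taken. Protocol 9.4.9.1 uses the mean of the 60- and 30-minute readings at baseline, names the same pair on later dosing days, and uses the mean of two at non-dosing visits.

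**Cohort 4.** The SAP is written to protocol v8.0 (Section 4), describes only 5 or 6 months of observation (6.1), and its schedule footnotes end at n (6.3). Protocol v9.0 has study drug on Day 1 only for Cohort 4 (7.2.4), 8 months of observation (3.7) and a footnote o that treats Visit 15 as a non-dosing visit (3.3).

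**The concern.** The SAP acknowledges the hold in disposition, exposure and compliance, but not in the displays that show effect over time. Protocol 1.7 says the Part A PK and PD data, including the follow-up after the last dose, will feed the modelling of doses and intervals for Phase 2. Duration of effect is the feature most easily blurred when one column mixes subjects at different times since their last dose, and there are only 6 active subjects per cohort.

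The spirometry rule is a separate problem that does not depend on the hold. Change from baseline is computed with one estimator at baseline and another at most later visits, so part of any apparent rise in lung function would come from the rule itself. The SAP also does not say which rule applies at a scheduled dosing visit where the dose was withheld.

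**Working it through.** **1. The plan's own figures.** 5 cohorts × 8 = 40 subjects (SAP Section 8). At 3:1, 8 × 3/4 = 6 active and 8 × 1/4 = 2 placebo. Each active subject carries 1/6 = 16.7% of a full cohort mean.

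**2. Does an affected subject leave the column?** The grouping rule in SAP Section 9 is limited by its parenthesis to dose or placebo. The Safety Population needs one injection; the PD Population adds a baseline and one post-baseline biomarker result. SAP 10.1.3 allows regrouping, but of whole cohorts. SAP 13.2 and 13.3 list no PD, CGI-C or ACQ-7 output by doses received or cut off after a missed dose. Retention is therefore the natural reading. The CGI-C and ACQ-7 tables are titled Safety Population although SAP 10.11 assigns the PD Population; neither set requires more than one injection.

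**3. How many visits follow a missed dose?** The source is protocol Tables 5 and 6 for the three-dose cohorts. Dosing on Days 1, 29 and 57 is my inference from the position of masked cells. PD assessments on dosing days are pre-dose (protocol 6.1).

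| Endpoint | Post-baseline visits | After missed third dose | After missed second dose |
|---|---|---|---|
| FeNO, spirometry | 10 | 6 | 7 |
| Eosinophils | 12 | 7 | 9 |
| CGI-C, ACQ-7 | 9 | 6 | 7 |

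These count later visits; they do not count altered results.

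**4. Time since last dose**, if visits stay on the Day 1 calendar:
- Day 85: 85 − 57 = 28 days if fully dosed; 85 − 29 = 56 if the third dose was missed; 85 − 1 = 84 if the second and third were missed.
- Day 225: 168, 196 and 224 days respectively.

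**5. Illustrative dilution.** Let m of 6 active subjects have lost doses and keep a share r of the full effect at a visit. Then column mean ÷ full-regimen mean = 1 − (m/6)(1 − r). Both m and r are assumptions; the documents give neither.
- m = 0: 100%.
- m = 1: 83% (r = 0) to 92% (r = 0.5).
- m = 2: 67% to 83%.
- m = 3: 50% to 75%.

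**6. Spirometry estimator.** For two readings X1 and X2, max = (X1 + X2)/2 + |X1 − X2|/2. If neither reading is systematically higher, a single reading and the mean of two have the same expectation, and the maximum exceeds both by E|X1 − X2|/2. With independent normal reading errors of SD s, E|X1 − X2| = 2s/√π, so the excess is s/√π ≈ 0.56s. A subject with no true change therefore shows an expected change of zero on dosing days and +0.56s on non-dosing days. The documents do not give s. SAP Section 11 lists three changes from the protocol, and this is not among them.

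**7. Cohort 4.** The planned-dose count, the all-doses-as-planned category and the status of Visit 15 depend on which document is followed. Under SAP 10.11.2, Visit 15 status also decides whether one reading or the larger of two is used there.

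**The case against.** **Modelling is planned.** The protocol synopsis and 9.4.8 say that PD markers, FEV1, CGI-C and ACQ-7 will be explored by exposure-response modelling, which can reflect doses not received and need not use column means. This partly stands. SAP 10.1.4 excludes formal analysis within the SAP, and the contents SAP 10.9 gives for the separate PK plan do not mention this modelling. Where it will be specified is unknown; it is not shown to be absent.

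**Retention is legitimate.** Protocol 3.9 and 4.9.2 encourage subjects who stop study drug to stay in the study, and an observed-data summary by group is a fair descriptive choice. Exposure tables and individual listings let a reader find the affected subjects. This stands as a reason to keep the all-subjects tables. The listings do not change the means or plots.

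**Key text cannot be seen.** Group labels are redacted, the table shells are not visible, and the blinded data review could settle the matter. This stands, so retention can only be said to appear. No rule on missed doses is stated for that meeting.

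**Visits may be realigned.** Protocol 3.9 realigns by time since last dose for subjects who had all expected treatments but missed observation visits. The day counts above do not hold for such subjects.

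**The spirometry bias is common to both arms.** It cancels on average against placebo subjects with the same dosing days and similar reading error. However, SAP 10.1.3 generally pools placebo across cohorts. On the inferred dosing days, Days 29 and 57 are dosing visits under protocol Table 6 but not under Table 8, and Day 85 is the reverse. Pooled placebo can then mix the two estimators at one visit.

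**Stronger readings.** A reader might infer that the columns cannot be read as the effect of the regimen, or that effects are diluted by 17% or more. The documents do not support either: if few active subjects lost doses, or only placebo subjects did, the active columns change little or not at all. Nor do they support inferring that the spirometry rule creates a false drug effect, since it applies to active and placebo alike.

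**Conclusion.** The point holds in two limited parts.

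First, the SAP's own planned-versus-expected distinction implies lost doses, and its by-visit PD, spirometry, CGI-C and ACQ-7 summaries appear to leave the affected subjects in their dose-group column to Week 32 with no supportive as-dosed display. The size is unknown. The 17% weight and the 50% to 92% range for m = 1 to 3 are illustrations, and no dilution at all (m = 0) is also possible. This part rests on reading redacted labels and unseen shells from the surrounding text, and the visit and day counts rest on inferred dosing days.

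Second, and more firmly, the SAP spirometry rule raises change from baseline at non-dosing visits relative to dosing visits for every subject, by half the average gap between the two readings. It contradicts protocol 9.4.9.1 and is undeclared. This rests only on the two readings having the same expectation.

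The Cohort 4 mismatch is secondary, but it affects the same dose counts and the same visit classification. Overall priority is low to moderate, because the endpoints are exploratory and no formal testing is planned.

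**What to change.** 1. **Spirometry.** Use one estimator at baseline and every later visit, namely the mean of the two readings as in protocol 9.4.9.1, whether or not a dose was given. If one reading is missing, use the other, as that section already allows. Both readings are already scheduled, so no new data are needed.
2. **Supportive display.** Keep the all-subjects tables and plots. Beside them, add a set for PD, spirometry, CGI-C and ACQ-7 that separates or omits visits after a dose missed in the hold, with n at each visit. The blinded team should define those visits from dosing records alone before unblinding, with the same rule for active and placebo; the blinded data review meeting is the natural place. Because the sponsor is unblinded throughout, record any part it has in this change in the appendix that SAP Section 4 provides for. Flag the affected subjects' later data, or show them by time since last dose, so that they are not discarded.
3. **Cohort 4.** Reconcile the SAP with protocol v9.0 so that planned-dose counts, compliance and Visit 15 status follow one regimen.

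**Cost.** One SAP amendment and one extra set of descriptive tables and plots. The supportive set has smaller n, and its membership changes between visits, so movement in a mean line may partly reflect who has left it. Say so in the footnotes; the all-subjects version beside it guards against misreading.
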